1.6.6 BMS-986016 handling and Dose Preparation following Nivolumab administration

As above, BMS-986016 infusion will be timed for 15-30 minutes after the completion of Nivolumab dosing. As with all injectable drugs, care should be taken when handling and preparing BMS-986016. Whenever possible, BMS-986016 infusions should be prepared in a laminar flow hood, glovebox, or safety cabinet using standard procedures for the safe handling of intravenous agents applying aseptic techniques. Gloves are required. If

BMS-986016 solution comes in contact with the skin or mucosa, immediately and thoroughly wash with soap and water.

Dose Preparation and Administration

Visually inspect drug product solution for particulate matter and discoloration prior to administration. BMS-986016 is a clear to slightly opalescent, colorless to pale yellow solution. Discard the vial if the solution is cloudy, discolored, or contains extraneous particulate matter other than a few translucent-to-white, proteinaceous particles. Do not shake the vial.

Preparation

• Withdraw the required volume of BMS-986016 and transfer into an intravenous container. BMS-986016 80 mg dose (8 ml BMS-986016 10 mg/ml solution) may be mixed with 52 ml NS to a total volume = 60 ml which can be infused over 60 minutes at 1 ml/min followed by flush.

Note: No incompatibilities between BMS-986016 injection and polyolefin or Non-DEHP IV components have been observed.

- Mix diluted solution by gentle inversion. Do not shake.
- Discard partially used vials or empty vials of BMS-986016

Storage of Infusion

The product does not contain a preservative. After preparation, store the BMS-986016 infusion either:

• at room temperature for no more than 4 hours from the time of preparation. This includes room temperature storage of the infusion in the IV container and time for administration of the infusion

or

• under refrigeration at 2°C to 8°C (36°F to 46°F) for no more than 24 hours from the time of infusion preparation. **Do not freeze.**

Note: the time needed for room temperature storage of the infusion in the IV container and time for administration of the infusion (up to 4 hours) must be subtracted from this 24 hour period. For example, a 1-hour infusion and 1-hour room temperature handling and storage will result in no more than 22 hours allowed under refrigeration storage.

Administration

Administer the infusion over 60 minutes through an intravenous line containing a sterile, non-pyrogenic, polyethersulfone low protein binding in-line filter (pore size of 0.2/0.22

micrometer). Do not co-administer other drugs through the same intravenous line. Flush the intravenous line at end of infusion with 0.9% Sodium Chloride Injection, USP (15-20 ml) to ensure that the total dose is administered. Total infusion and flush time should equal to 60 minutes.

NOTE: When dosing sequentially with Nivolumab, the BMS-986016 infusion should begin within 15 to 30 minutes after the end of the Nivolumab infusion.

1.6.7 Infusion monitoring for combination of Nivolumab and BMS-986016

Monitoring for an infusion reaction and cytokine release on Day 17 (+/-2 days) of the protocol will consist of clinical observation in the day hospital ward or 7SW of the NIH Clinical Center. The total infusion monitoring time will be expected to last 4-5 hours for most patients. First, the patient will receive Nivolumab as an IV infusion over 30 minutes. Patients with a prior Grade 2 or 3 infusion reaction will have pretreatment with 25mg of Benadryl IV together with 650mg of Tylenol PO. During both infusions, patients will have q15 minute vital signs, including temperature, pulse, blood pressure and pulse oximetry. BMS-986016 infusion will begin 15-30 minutes after completion of the Nivolumab infusion. BMS-986016 will then be given as an IV infusion over 60 minutes with ongoing monitoring. The patients will also be monitored for two hours after completion of the BMS-986016 in the day hospital or 7SW. Specifically, we will be checking the patients for fever, chills, shakes, itching, rash, hypertension or hypotension or difficulty breathing during the administration or immediately afterwards (within the following 2 hours). The patients will be treated according to I-O AE Algorithms from Appendices B and C; Investigator Brochures for Nivolumab (BMS-936558) and Relatlimab (BMS-986016). Generally, Grade 1 infusion reactions will be observed. Grade 2 or 3 infusion reactions will prompt interruption of the patient's infusion until the observed symptom returns to the level of a Grade 1 reaction. Patients will be given 25mg of Benadryl IV and 650 mg of Tylenol PO for any grade 2 or 3 reaction. The Benadryl can be repeated once for symptom resolution until the reaction returns to a level of Grade 1. If a patient has a Grade 2 or 3 reaction, subsequent infusions will be preceded by 25mg of Benadryl IV and 650mg of Tylenol PO 30 minutes prior to dosing. Grade 4 reactions will cause discontinuation of the therapy. Patients will be instructed to inform the clinical team of any symptoms including, but not limited to, fever, chills, itching, shortness of breath, stomach discomfort, diarrhea, new neurological symptoms, seizures, changes in urinary function, chest pain, palpitations, rashes or any other significant concern in between drug doses.

1.6.8 Clinical Pharmacokinetics

An interim determination of BMS-986016 multiple dose PK was carried out using all available serum concentration data from Studies CA224020 and CA224022. Noncompartmental analysis was performed using concentration-time data after the first dose (Cycle 1) and ninth dose (Cycle 3). In general, the maximum observed concentration (Cmax) and area under the concentration versus time curve over the dosing interval (AUC[TAU]) values over the first dosing interval increased approximately proportional to the increment in the BMS-986016 dose. BMS-986016 accumulation from the first to ninth doses of a Q2W regimen was around 2- to 3-fold for AUC(TAU) and 1.2- to

1.8-fold for Cmax. BMS-986016 effective half-life was estimated to be approximately 20 days. The PK of BMS-986016 or nivolumab were not altered when given in combination.

BMS-986016 population PK was best described by a 2 compartment model with parallel linear and non-linear CL. The linear portion represents the non-specific clearance (CL), and non-linear component represents target-mediated CL. The linear CL was 0.18 L/day, and the volume of distribution in the central compartment was 4.5 L. The maximum rate of non-linear elimination (Vmax) was 2.5 mg/day, and the concentration that achieved 50% of Vmax (Km) was 5.7 μ g/mL.

Currently available data suggest that BMS-986016 monotherapy exhibits a low level of immunogenicity, with 6 out of 42 subjects having at least 1 post-baseline positive ADA samples. There are limited data available in combination cohort to make inference on immunogenicity rate.

1.6.9 Clinical Safety

As of the clinical cutoff date of 15-Jul-2020, treatment with BMS-986016 in combination with nivolumab has been administered to 1332 subjects. Treatment-related AEs were reported in 890 (66.8%) subjects, with the most commonly reported (\geq 5% of subjects) being fatigue (15.5%), pruritus (7.4%), diarrhea (8.6%), asthenia (7.4%), rash (7.1%), arthralgia (7.5%), hypothyroidism (7.2%) and increased lipase (6.5%). Most drug-related AEs were Grade 1-2. Grade 3-4 drug-related AEs were reported in 199 (14.9%) subjects, and 2 (0.2%) subjects reported Grade 5 events (dyspnoea and pulmonary fibrosis). The types of treatment-related AEs, as well as the rates of treatment-related AEs, appeared comparable to historical nivolumab monotherapy rates. All treatment-related AEs, except for 1 Grade 4 myocarditis (240 mg relatlimab/240 mg nivolumab Q2W), as well as 1 Grade 4 potential drug-induced liver injury, 1 Grade 5 dyspnea, and 1 Grade 3 pneumonitis (all at a dose level of 80 mg relatlimab/240 mg nivolumab Q2W), were reversible and manageable by withholding study treatment administration, providing standard medical care, and/or following immune-related AE algorithms. Safety results to date indicate that sequential, coadministration, and the FDC of relatlimab + nivolumab have similar safety profiles.

1.7 Microdialysis for cytokines

Microdialysis has been well established for 25 years as a safe, reliable way of measuring the *in vivo* concentrations of various molecules in the microenvironment of various human tissues, including the brain[30]. The probes, which can be implanted directly into the brain through minimally invasive openings into the skull, are catheters which contain small semi-permeable membranes at their tips that allow the diffusion of small molecules in and out of the probe[31]. By slowly infusing isotonic fluids in and out of the system, the levels of various solutes within the brain can be determined without the need for multiple biopsies of the area of interest. Initial work in the brain focused mostly on

neurotransmitters and on changes in their levels in specific areas of the brain in response to various stimuli. The technique of placement of these probes within the brain has been performed safely for years [32]. Due to research on the inflammatory response to trauma, there is a well-established body of literature on the practice of recovery of cytokines from the brain by dialysis, and this has recently been safely applied to brain tumor patients[33]. In this study, interferon gamma levels were undetectable after the inflammatory response to surgery had died down. These soluble factors can give a real-time accounting of the inflammatory response to an insult in the brain, giving a level of detail about reactions to immune stimuli that would be completely unattainable by other methods.

For our study, we propose the use of microdialysis to determine if checkpoint inhibitors have their desired effect in the tumor microenvironment. Presently, an anti-tumor immune response is suspected when serial MRI imaging over several months documents initial increase in tumor enhancement, signifying an inflammatory response to therapy, followed by reduced volume of enhancing tumor indicating tumor regression. Interpretation of anti-tumor response by MRI is complex because the MRI appearance of an inflammatory response to immunotherapy can appear similar to that of tumor recurrence or growth. Instead of waiting months to determine if an immune response to the tumor has occurred, we intend to use microdialysis of cytokines as a real-time test to measure immune response to a checkpoint inhibitor shortly after its administration, providing an answer within days of the first dose. Recent study in mice has shown that PD-1 blockade leads to an upregulation of interferon gamma production in circulating T lymphocytes responding to an infection[34], and this agrees with previous research that shows that interferon gamma is upregulated when PD-L1 is blocked in vitro[35]. Further, in recurrent glioblastoma patients, there is evidence that regulatory T cells in the systemic circulation of these patients release increasing amounts of IFNg (interferon gamma) in response to nivolumab[36]. Of note, other markers of cytotoxic activity, such as Granzyme A and Perforin 1, are much larger proteins than IFNg, and as such reliable recovery of this proteins by microdialysis is unlikely. As such, our hypothesis is that checkpoint blockade with Nivolumab will lead to an upregulation of the inflammatory cytokine interferon gamma in the tumor microenvironment as measured by cerebral *microdialysis*. After the intensive inpatient monitoring period, patients will be placed on combined therapy of BMS-986016 and Nivolumab in combination. In this way, we will be able to continue to follow immune cell populations in the blood of patients, so that we can determine if the systemic effects of checkpoint blockade differ between patients on Nivolumab versus patients on the combination of Nivolumab and BMS-986016 treatment.

1.8 Conclusion

This protocol seeks to enroll patients with recurrent glioblastoma for treatment with nivolumab and for immune monitoring with cerebral microdialysis. Currently, there is not an established standard of care for these recurrent glioblastoma patients, and so they will not be forgoing any proven therapeutic options. The study is designed primarily to discover whether interferon gamma will be produced within the brain in response to

systemic checkpoint inhibitor therapy. Patients will undergo a surgical procedure that includes brain tumor needle biopsy to confirm the diagnosis of recurrent glioblastoma. If the diagnosis of recurrent glioblastoma is confirmed by frozen section, they will proceed with the remainder of the protocol. If this diagnosis cannot be definitively confirmed on frozen section, the patient will not proceed with the placement of microdialysis catheters or lumbar drain. If the patient does have frozen section evidence of recurrent glioblastoma, 2 microdialysis catheters will be implanted, one into the tumor, and one into the surrounding brain. A lumbar intrathecal catheter will also be inserted to serial sample cerebral spinal fluid (CSF). A bone marrow examination may be performed to evaluate the baseline status of the patients' hematopoietic tissue. To allow the inflammatory response to catheter implantation to subside, we will wait two days after surgery before administering the PD-1 inhibitor, Nivolumab. We will then take samples every 6 hours from the microdialysis catheters, and daily samples from blood and cerebral spinal fluid. At the end of five days, we will remove the dialysis catheters and lumbar intrathecal catheter and resect the recurrent glioblastoma tumors. A repeat bone marrow examination may be performed to evaluate if Nivolumab causes any changes in the patients' hematopoietic tissue. Following tumor resection, the patient will receive Nivolumab and an anti-LAG-3 antibody, BMS-986016, until tumor progression or until the patient experiences an immune mediated toxicity that prevents further treatment, as defined in Appendix A. We will analyze the cerebral spinal fluid, microdialysis fluid and blood for immune markers by proteomic analysis. We will measure changes in immune markers in the various compartments (brain tumor, brain, blood, CSF and potentially bone marrow) between before and after their first dose of nivolumab and determine the relative immune effects of Nivolumab in these compartments. Recent data in melanoma patients suggests that after a month of treatment, changes in histological markers of immune response such as cluster of differentiation 8 (CD8), CD4, CD3, PD-1, PD-L1 and lymphocyte activation gene 3 (LAG3) may be predictive of response to PD-1 inhibitors[37]. As such, if we are unable to establish interferon gamma as a suitable marker of immune response, we will evaluate pathological response as our primary outcome measure.

The relationship between markers of inflammation in the interstitial fluid, cerebral spinal fluid and serum have been investigated by the neuroimmunology community for years, but there are many answers left to be unlocked. This protocol aims to gather a truly unprecedented collection of data which could be used to better understand the unique immune environment of the brain as compared to the rest of the body. Potential gains could be a better understanding of how cerebral spinal fluid samples reflect changes in the immune microenvironment of the brain – is there a reliable relationship between cytokine levels in the interstitial fluid and cerebral spinal fluid, or are they completely different and unrelated? Are there other proteins that are better predictors of the nature of the immune populations in the brain? Are there serum markers that better predict intracranial inflammation than CSF markers do? Such findings could be applied to other neuroinflammatory disorders, such as multiple sclerosis or cryptococcal meningitis. The technique of microdialysis for cytokines, using proteomic analysis of the dialysates, which has not been done, could be applied to other disorders as well. For all of these reasons, while we feel that this protocol may provide critical information in the treatment

of brain tumors, we also feel that the study has the potential to create generalizable knowledge that will have a high impact in the scientific community. The National Institutes of Health Clinical Center is the only institution that is perfectly positioned to perform a trial such as this with the potential to truly revolutionize how we view inflammation in the brain.

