2.2 Exploratory Goals

1) To determine the change in interferon gamma production within the tumor microenvironment and in the rest of the body from before and after therapy with the immune checkpoint inhibitor, nivolumab;

2) To evaluate the pathological response of the immune microenvironment of brain tumor tissue to the first dose of Nivolumab;

3) To evaluate the clinical response (progression free survival, overall survival) of recurrent glioblastoma patients to treatment with BMS-986016 and Nivolumab;

4) To describe the difference in survival between responders and non-responders;

5) To examine the differences in the immune cells and secreted factors of the tumor environment as compared to the immune cells and secreted factors of the cerebral spinal fluid, blood and potentially bone marrow in response to this treatment;

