4.4 Study Design

This protocol is an open label, non-blinded single armed pilot study of the use of nivolumab and BMS-986016 in recurrent glioblastoma patients.

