At the time of surgery, adults will be admitted to the Neuroscience Patient Care Unit (NPCU). The patient will be asked to sign a standard surgical consent form that covers the tumor biopsy, microdialysis probe placement, and lumbar drain placement. These surgical procedures will be considered the beginning of Phase 1 of the trial for safety monitoring purposes. For the research surgical procedure, on study day 1, the stereotactic biopsy will be performed using frameless stereotaxy. A frozen section will be sent from the biopsy tissue. If the biopsy confirms recurrent tumor, the patient will continue with study procedures. If the biopsy is not consistent with recurrent tumor, the patient will not undergo further study procedures and will be replaced. The burrholes for the microdialysis catheters will be placed using stereotactic guidance in a similar fashion to the biopsy procedure. Lumbar drain placement will also be performed in this same surgical procedure. While the patient is under anesthesia, a hematology fellow may perform a bone marrow examination. Following biopsy and microdialysis catheter implantation, subjects will stay in the ICU for 24 hours, and then be moved to a private inpatient room with a one-on-one sitter until the time of resection, 7 days after the initial biopsy. The first dose of Nivolumab will be given at 48 hours after the biopsy on study day 3. The lumbar drain catheters will remain clamped in between CSF sampling to allow the patients to be mobile during their inpatient stay. A stereotactic CT scan will be performed after the biopsy and microdialysis catheter placement to verify accurate placement and assess for procedural complications. Phase 1 will end at the start of surgical resection of the tumor, and clinical care will then commence as outlined below. Primary outcome measures will be assessed at the conclusion of enrollment, as all samples will be sent for cytokine testing at that time. All patients will come for a safety monitoring visit 2 weeks after their second surgery (+/-1 week) for safety evaluation. All patients will continue with routine examinations and Nivolumab and BMS-986016

therapy every 2 weeks, starting on study Day 17 (+/- 2 days) until recurrence or a dose limiting toxicity is experienced with appropriate imaging.

4.5.2 Summary of Clinical Care Procedures and follow up (Study Phase 2):

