9.0 Outcome Measures

9.1 Primary outcome measure

The primary outcome measures are:

- 1. The proportion of patients that have a rise in interferon gamma levels within the tumor microenvironment of 4 pg/ml or higher before the first dose of Nivolumab as compared to the 5th day after treatment with Nivolumab.
- 2. The safety of the use of microdialysis catheters for immune monitoring in recurrent glioblastoma patients
- 3. The safety of the combination of nivolumab and BMS-986016 in recurrent glioblastoma patients

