9.2 Exploratory outcome measures

Exploratory outcome measures and include:

- 1. The change in interferon gamma expression from before, during and after Nivolumab treatment in the brain microenvironment, cerebral spinal fluid and the blood.
- 2. The difference between the IHC staining for CD3, CD4, CD8, CD20, CD45RO, CD57, CD68, FOXP3, Granzyme B, LAG3, PD-1, CD14, CD33, CD163, and CD206 before and after Nivolumab therapy. These markers will be evaluated as density of cells, defined as the number of positive cells per mm². PD-L1 expression will be evaluated in tumor cells using H-score, which includes the percentage of positive cells showing membrane staining pattern (0–100) multiplied by the intensity of the staining (0 to 3+), with a total score ranging from 0 to 300. The final score for each marker will be expressed as the average score of the areas analyzed within the tumor region (tumor center).
- 3. Progression free survival and overall survival of recurrent glioblastoma patients after treatment. Progression free survival is defined as the time length from the first dose of study drug with recurrence to progression as defined by iRANO criteria, and the overall survival is defined as the time length from the first dose of study drug to death. If a lesion is 25% larger but there remains a question as to disease progression or pseudoprogression due to treatment, the patient can remain on treatment until this can be defined. If true progression occurred earlier, the earlier date will be used for censorship. If patient is lost to follow-up prior to documented progression or death, patient will be censored as of the date of the last adequate evaluation (MRI and exam). If patient dies prior to documentation of progression, progression will be defined as the date of death, if patient has been attending regularly scheduled follow-ups.
- 4. The difference in progression free survival and overall survival between patients who have an interferon gamma response versus those that do not have one.

5. The difference in the immune cells and secreted factors of the tumor environment as compared to the immune cells and secreted factors of the cerebral spinal fluid, blood and potential bone marrow in response to this treatment

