10.0 Statistical Analysis

10.1 Data analysis

Primary goals

- To determine the proportion of patients who have an increase of interferon gamma production within the tumor microenvironment from before and after therapy with the immune checkpoint inhibitor, nivolumab. The change will be dichotomized as increase vs. no increase with the threshold of 4pg/ml. The proportion of the patients with increase will be evaluated by exact binomial test.
- To evaluate the safety of using brain tumor microdialysis to monitor response to immune modulators in patients with recurrent glioblastoma.
 Descriptive statistics, such as frequency and percentage, will be used to evaluate the safety of these procedures.
- To evaluate the safety of the combination of Nivolumab and BMS-986-016 in the treatment of recurrent glioblastoma patients.
 Descriptive statistics, such as frequency and percentage, will be used to evaluate the safety of these treatments.

Exploratory Goals

1) To determine the change in interferon gamma production within the tumor microenvironment and in the rest of the body from before and after therapy with the immune checkpoint inhibitor, nivolumab.

A one-sample t-test or Wilcoxon signed rank test will be performed to evaluate the change (continuous) over time (between pre- and post-treatment) in the outcome measures

2) To evaluate the pathological response of the immune microenvironment of brain tumor tissue to the first dose of Nivolumab

A one-sample t-test or Wilcoxon signed rank test will be performed to evaluate the change between pre- and post-treatment for each marker evaluated.

3) To evaluate the clinical response (progression free survival, overall survival) of recurrent glioblastoma patients to this treatment

The Kaplan-Meier method will be used to estimate the survival function and generate survival curves. The study is not powered to detect significant differences in survival between the patients in this cohort and historical controls.

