10.2 Power analysis

The power analysis was performed using the primary outcome, which is defined as increase vs. no increase based on the difference in expression of interferon gamma between baseline and the 5th day after nivolumab treatment with the threshold of 4pg/ml. The hypothesis is that the proportion of the patients with increase is greater than 0.2. The expected proportion is 0.7. The following table shows the estimated power based on 10 subjects for different null and observed proportions using the two-sided exact binomial test.

Null	Expected	Actual	Estimated
Hypothesis	Proportion	Alpha	Power
0.1	0.9	0.0128	>.999
	0.8	0.0128	>.999
	0.7	0.0128	0.989
	0.6	0.0128	0.945
0.2	0.9	0.00637	0.998
	0.8	0.00637	0.967
	0.7	0.00637	0.85
0.3	0.9	0.01059	0.987
	0.8	0.01059	0.879
0.4	0.9	0.01834	0.930

Table 6 - The estimated power of 10 subjects for different null and observed proportions

Table 6 indicates that a sample size of 10 subjects: (a) will have 85 power to reject the null hypothesis: $p \le 0.2$ when ≥ 7 subjects are found to have increased interferon gamma in five days after the treatment and (b) will have 93.0% power to reject the null hypothesis: $p \le 0.4$ when ≥ 9 subjects are found to have increased interferon gamma.

Observed	95% CL	
proportion		
1	0.6915	1
0.9	0.555	0.9975
0.8	0.4439	0.9748
0.7	0.3475	0.9333 (a)
0.6	0.2624	0.8784
0.5	0.1871	0.8129
0.4	0.1216	0.7376
0.3	0.0667	0.6525

Table 7 - 95% confidence limits (CL) for proportions with a sample size of 10 subjects.

Table 7 presents the 95% confidence limits for the observed binomial proportion 0.3 to 1.0 based on a sample size of 10 subjects. For a sample size of 10 subjects, if 7 subjects are observed with increased interferon gamma in five days, the interval of (0.35, 0.93) will have 95% probability to include the true proportion (a).

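### Section 1.8 lets pathological response replace interferon gamma as a primary outcome on an undefined judgement that could be made after the results are seen

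*Combined protocol and SAP*

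**What the plan says.** Section 1.8 closes its outline of the study with a contingency: if the team is "unable to establish interferon gamma as a suitable marker of immune response, we will evaluate pathological response as our primary outcome measure". No other section repeats it.

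The sections that govern outcomes and analysis say something else:

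- Section 2.1 names the interferon gamma proportion and two safety goals as primary, with no alternative.
- Section 9.1 lists as its first primary outcome: "The proportion of patients that have a rise in interferon gamma levels within the tumor microenvironment of 4 pg/ml or higher".
- Section 10.1 tests that proportion with an exact binomial test, and section 10.2 is built on the same endpoint: "The power analysis was performed using the primary outcome, which is defined as increase vs. no increase".
- Section 2.2 places this among the exploratory goals: "To evaluate the pathological response of the immune microenvironment of brain tumor tissue to the first dose of Nivolumab".
- Section 9.2 gives the corresponding exploratory measure, a comparison of pre-dose with post-dose tissue: "The difference between the IHC staining for CD3, CD4, CD8, CD20, CD45RO, CD57, CD68, FOXP3, Granzyme B, LAG3, PD-1, CD14, CD33, CD163, and CD206". It adds PD-L1, scored by H-score.
- Section 10.1 gives the exploratory analysis: "A one-sample t-test or Wilcoxon signed rank test will be performed to evaluate the change between pre- and post-treatment for each marker evaluated".

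On timing, section 4.5.1 says: "Primary outcome measures will be assessed at the conclusion of enrollment, as all samples will be sent for cytokine testing at that time".

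**The concern.** The same endpoint is exploratory in three sections and conditionally primary in a fourth. The condition is open: the plan gives no meaning for a suitable marker, no decision-maker and no time for the decision. It has no detectability, recovery or missing-sample criterion that would separate a failed assay from a true negative. Because the cytokine samples are all assayed once enrollment is over, any judgement of suitability that rests on this trial's data can only follow those data. I found nothing that fixes when the tissue is read, so the pathology could be known by then too.

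A null or undetectable interferon gamma result could thus be described as a marker problem. A favourable tissue marker could then be reported as the primary finding, with section 1.8 cited as pre-specification. The binomial test, alpha and power of section 10.2 would not describe that claim.

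The fallback is also not ready to serve as a primary. Section 9.2 gives a metric for each marker, but no section gives a lead marker, an alpha, a multiplicity rule or a definition of success.

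**Working it through.** **1. Status of each endpoint, section by section.**

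| Section | Interferon gamma proportion | Pathological response |
|---|---|---|
| 1.8 | primary unless judged unsuitable | primary if interferon gamma is judged unsuitable |
| 2.1, 9.1 | primary, no contingency | not listed |
| 2.2, 9.2 | change over time only, exploratory | exploratory |
| 10.1 | primary, exact binomial | exploratory, one test per marker |
| 10.2 | sole basis of the power analysis | not mentioned |

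**2. The plan's own figure.** Inputs from section 10.2: n = 10, null proportion 0.2, expected proportion 0.7, two-sided exact binomial. The lower tail is empty, since P(X = 0 | 0.2) = 0.8^10 = 0.107 exceeds 0.025. The rejection region is X ≥ 6:

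- Alpha = P(X ≥ 6 | 10, 0.2) = 0.00551 + 0.00079 + 0.00007 + 0.00000 + 0.00000 = 0.00637, as in Table 6.
- Power = P(X ≥ 6 | 10, 0.7) = 0.850, as in Table 6.

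(The text under Table 6 ties this power to 7 or more patients. The exact power at that cut-off is 0.650. That is a separate matter.)

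These figures belong to interferon gamma alone.

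**3. How often the planned test would miss.** P(X ≤ 5 | 10, p) is 0.994 at p = 0.2, 0.623 at p = 0.5 and 0.150 at p = 0.7. Even at the expected proportion, about one trial in seven would fail to reject, which is the situation in which a switch would be tempting.

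**4. What an open switch could do to the false-positive rate.** Section 1.8 does not define pathological response. I take it to mean the panel in section 9.2, because sections 2.2 and 10.1 use the same term for it.

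- Panel in 9.2: 15 stained markers + PD-L1 = 16.
- Markers named as examples in 1.8: CD8, CD4, CD3, PD-1, PD-L1, LAG3 = 6.
- Assumptions that are not in the plan: two-sided 0.05 per marker, and success if any one marker is significant.

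Independent markers: 1 − 0.95^6 = 0.265 and 1 − 0.95^16 = 0.560.

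Correlated markers: 40,000 simulated null trials, n = 10, equicorrelated normal changes, one-sample t-test.

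| Pairwise correlation | 6 markers | 16 markers |
|---|---|---|
| 0 (formula) | 0.265 | 0.560 |
| 0.3 | 0.246 | 0.492 |
| 0.5 | 0.216 | 0.400 |
| 0.7 | 0.174 | 0.291 |
| 0.9 | 0.114 | 0.159 |

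The signed rank test (reject when the smaller rank sum is 8 or less, exact level 0.0488) gives 0.239 to 0.118 for 6 markers and 0.490 to 0.167 for 16, over correlations of 0.3 to 0.9.

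Section 10.1 leaves the choice between the two tests open. If either may be used for each marker, the rates at correlations 0, 0.3 and 0.9 become 0.295, 0.271 and 0.130 for 6 markers, and 0.604, 0.534 and 0.180 for 16. That adds about 2 to 4 points.

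**5. The two-step procedure.** Suppose interferon gamma is tested first at its actual alpha and the tissue is read only if that test fails. With all tests independent, the chance of at least one nominally positive primary is 1 − (1 − 0.00637) × 0.95^k:

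- k = 1: 0.056
- k = 6: 0.270
- k = 16: 0.563

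If the k markers are perfectly correlated with one another, the figure is 0.056 whatever k is. The range is therefore about 0.06 to 0.56, against 0.00637 planned.

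**The case against.** The strongest defence is that this is one conditional sentence in an introduction, while the sections on objectives, outcomes and statistics agree with one another. Under section 10.1 a patient who does not reach the 4 pg/ml threshold is already counted as having no increase, and nothing in 1.8 cancels that analysis. The sentence may be meant for a measurement failure only. This is also a ten-patient pilot with two descriptive safety primaries that are not touched.

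Much of that is fair. The interferon gamma analysis would still be run. What section 1.8 changes is which result may be called primary, and the benign reading is not written down. Although it is a pilot, section 10.2 sets a formal hypothesis, test and power.

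Some supporting points deserve limited weight. "This protocol is an open label, non-blinded single armed pilot study" adds little, because everyone receives the drug; the timing of the assay is what matters. Section 1.7 reports an earlier brain tumor microdialysis study in which interferon gamma became undetectable once surgical inflammation settled. That makes an undetectable result conceivable, but a low background is equally compatible with detecting a rise after nivolumab.

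The percentages depend on an alpha and a success rule that the plan does not contain, and the six markers in 1.8 are examples, not a defined set. The figures illustrate the risk and are not this trial's error rate.

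Finally, interferon gamma could be unmeasurable because catheters fail, are removed early or stop flowing (sections 4.5.12 and 8.1.1), with replacement limited by the accrual ceiling of 25 (section 3.1). A trigger of that kind could be legitimate if set in advance, but section 1.8 does not state one.

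**Conclusion.** The concern holds. Section 1.8 conflicts with sections 2.1, 2.2, 9.1, 9.2, 10.1 and 10.2. As written, it permits a change of biological primary outcome that depends on the result, to a panel with no ranking and no error control. The contradiction and the open trigger follow from the text alone.

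The size rests on the assumptions stated in the check. With 16 markers the chance of at least one false positive is about 56% under independence and 49% down to 16% at correlations of 0.3 to 0.9. With the 6 markers named in 1.8 it is about 26%, and 25% down to 11%. One pre-named marker with one pre-named test would give 5%. This should be fixed before any cytokine sample is assayed.

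**What to change.** Delete the sentence in section 1.8, and add a sentence to sections 9.1 and 10.1 stating that pathological response stays exploratory whatever the interferon gamma result. The cost is one deletion and one clarifying sentence in each of the two sections. The downside is that if interferon gamma cannot be measured, the trial has no biological primary result, only the two descriptive safety primaries.

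If the sponsor wants a fallback, write it into 9.1, 10.1 and 10.2 before any sample is assayed:

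- one marker, with its section 9.2 metric;
- one test at a stated alpha, and one success criterion;
- a trigger based on assay quality control, such as failed calibration or spike-recovery controls;
- a statement that low or undetectable patient levels with passing controls are a result, not a trigger;
- who applies the trigger, and when.

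Loss of samples through catheter failure could be a second trigger, provided it is defined in advance and applied without reference to interferon gamma values. This option costs a short paragraph. It should also justify the choice of marker, because the rationale in 1.8 cites tissue changes after a month of treatment, whereas here the tumor is resected five days after a single dose.
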